6.3.8 Viral Disease Screening

Subjects will be tested for HIV, hepatitis B, and/or hepatitis C to determine eligibility at screening visit.

HBsAg, HBcAb, HCV, and HIV are to be determined by each site's local laboratory.

Note: For HBcAb, site is requested to perform HBcAb IgG and HBcAb IgM. If any of these 2 results is positive, then the subject will be considered as screen failure.

6.4 Pregnancy

Pregnancy itself is not regarded as an AE unless there is a suspicion that the study treatment may have interfered with the effectiveness of a contraceptive medication. If a pregnancy is reported for a subject, no further study treatment will be administered to this subject and the outcome of all pregnancies (spontaneous miscarriage, elective termination, normal birth, or congenital abnormality) must be followed up and documented. Follow-up should be done up to delivery and after the examination of the newborn a follow-up report should be sent with any new information regarding the pregnancy and the outcome of the newborn.

All congenital abnormalities/birth defects should be classified as SAEs. Spontaneous miscarriages should also be reported and handled as SAEs. Elective abortions without complications should not be handled as SAEs but should be reported as an AE. All outcomes of pregnancy must be reported to the sponsor on a pregnancy outcomes report form.

Pregnancy outcomes must be collected for the female partners of any males who took study treatment in this study. Consent to report information regarding these pregnancy outcomes should be obtained from the female partner.

Pregnancies must be reported to the sponsor or sponsor's designated safety services using the reporting details provided in [Section 6.3.1.5](#) within 24 hours of awareness.

6.5 Blood Loss During the Study

For the safety evaluation, approximately 10 mL of blood will be withdrawn from the subjects at each time point. A total of approximately 145 mL of blood will be collected per subject during the study for immunogenicity, for estimation of rituximab concentration, and safety evaluation as mentioned in [Table 6-1](#).

Table 6-1: Blood Loss During the Study

Time Points	Safety Evaluation (Laboratory)	ADA and NAb Evaluation	For Estimation of Rituximab Concentration (Approximately)	Total Volume of Blood Loss
Screening	10 mL	-		10 mL
Week 1/Day 1	10 mL	10 mL	5 mL	25 mL
Week 2/Day 15	10 mL	10 mL	5 mL	25 mL
Week 4	10 mL	10 mL	5 mL	25 mL
Week 8	10 mL	10 mL	5 mL	25 mL
Week 12	10 mL	10 mL	5 mL	25 mL
Week 26	10 mL	-	-	10 mL
Total volume of blood loss	70 mL	50 mL	25 mL	145 mL

Abbreviations: ADA, anti-drug antibody; NAb, neutralizing antibody.

Note: For safety evaluation, more than 10 mL of blood can be withdrawn based on the site/local laboratory practice and will not be considered as a deviation.

[figure not shown]
7 Statistical and Analytical Plan

7.1 Sample Size Calculations

CI

CI

7.2 Analysis Sets

The safety population will include all subjects who are randomized and receive at least 1 dose of study treatment.

Immunogenicity population will include all subjects with at least 1 post-dose ADA assessment result available.

Analyses of safety parameters will be based on the safety population, and immunogenicity parameters (ADA and NAb) will be based on the immunogenicity population.

7.3 Description of Subgroups to be Analyzed

Immunogenicity and key safety parameters will be presented overall and by region, as appropriate.

7.4 Statistical Analysis Methodology

7.4.1 General Principles

The statistical analysis will be performed using SAS Version 9.4 or later.

The immunogenicity and safety data will be analyzed descriptively. All individual data as well as results of statistical analyses, whether explicitly discussed in the following sections or not, will be presented in individual subject data listings and statistical summary tables.

In general, continuous variables will be summarized using the following standard descriptive summary statistics: number of observations, arithmetic mean, standard deviation, minimum, median, and maximum. Categorical variables will be displayed by means of frequency tables including percentages.

Baseline is defined as the last non-missing pre-dose assessment. Overall summaries and analyses will be performed based on data pooled from all sites.

A SAP will be prepared and finalized before the clinical study database is closed.

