4.1.1 Inclusion Criteria

A subject will be eligible for enrolment in the study if he/she meets all of the following criteria:

1. Male or female subjects aged 18 years or older who have provided valid written informed consent.
2. Subjects with a diagnosis of active RA who are eligible for the subsequent treatment course with US-rituximab or EU-rituximab according to the clinical judgment of the investigator.
3. Documented evidence that subject has received at least 1 full course comprising two 1000 mg infusions of either US-rituximab at least 16 weeks prior to the randomization visit or EU-rituximab at least 24 weeks prior to the day of randomization visit.

Note: Subjects are only eligible if they have received the prior US or EU-rituximab course within the 15 months prior to the date of randomization.

4. Subjects receiving a stable dose of weekly MTX for at least 4 weeks prior to randomization (between 7.5 mg and 25 mg) and folic acid (at least 5 mg per week).

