4.2 Withdrawal of Subjects From Study Treatment and/or the Study

The duration of the study is defined for each subject as the date when signed written ICF is provided through the EOS visit on Week 12. An additional follow-up visit will be conducted at Week 26 to evaluate safety and to perform a serum pregnancy test in WOCBP. Subjects having signed the ICF versions prior to the one introduced by this amendment need to re-consent to continue participating in the study after Week 12 through Week 26. If a subject does not re-consent for further study participation after Week 12, then his/her study data up to Week 12 will be collected and the subject will be discontinued from the study.

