6.2.2 Immunogenicity Assay

Immunogenicity samples will be analyzed by designated analytical laboratory(ies) using validated methods. Analysis of ADA samples will follow a tiered approach of screening, confirmation, and titer determination. Samples that are confirmed positive for ADA will be further tested for titer and NAb using validated assays.

Immunological testing in human subjects will involve a multi-tiered approach as outlined below:

Tier I Screening Assay: All the clinical samples for immunogenicity assessment will be subjected to a screening assay. The methodology is based on the principle of capture of the ADA by the drug and detection by biotin-labelled drug, using ELISA. The test methodology may be modified after the method validation is completed. During method validation, an assay cut point is statistically determined. The samples that show a response equal to or above the pre-determined screening cut point will be called as “screening positive” and the ones that show a response below the assay cut point will be called as “negative”.

Tier II Confirmation Assay: All the clinical samples that are “screening positive” will be subjected to a confirmation assay. This will involve the inhibition of the response seen in the screening assay with high concentration of drug. The assay format is an adaptation of the screening assay, where the samples are spiked with phosphate-buffered saline or drug and incubated for 1 hour at 37°C prior to evaluation according to the screening assay procedure. The samples that show a response equal to or above the pre-determined confirmatory cut point will be called as “confirmed positive” and the ones that show a response below the assay cut point will be called as “negative”.

[figure not shown]
Tier III Titer Determination: It is the semi-quantitative assay where titers of the confirmed ADA-positive samples will be evaluated with respect to a previously established titer cut point. During the clinical sample analysis, serial 2-fold dilutions of confirmed positive samples will be performed and the reciprocal of the dilution able to yield a response at or above the titration cut point will be reported as the titer of the ADAs.

Tier IV Neutralizing Antibodies Assay: This is based on the principle that any sample containing NAbs would reduce or abolish the biological activity associated with a known concentration of drug product used in a cell-based NAb assay. This is based on the mechanism

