8.1. Analysis of Immunogenicity Endpoints

Blood samples for detection of ADA (including NAb) will be collected prior to initiation of the infusion (preferably within 30 minutes before initiation of the infusion) of study treatment on Day 1 and Day 15 and then on visits at Weeks 4, 8, and 12 (EOS/ET).

Summary statistics (frequency and percentage) by treatment arm and overall will be provided for the percent of subject with ADA formation at Day 1 and Day 15, and at weeks 4, 8, 12 (EOS/ET) visit. A subject is considered as ADA positive during the study if the subjects had at least one ADA positive sample otherwise the subject is regarded as ADA negative. Note this will also include any unscheduled visits during the study period.

Additionally, for subjects who are ADA positive at baseline, a shift table per treatment arm will be generated. The shift table includes numbers in each class (decreased, stable, and increased) as well as percentages relative to the number of ADA positive subjects with an available evaluation at the specific visit.

Subjects will be classified at each visit post baseline as:

- Decreased: If ADA titer at post-baseline visit decreases to a lower titer than that observed at baseline. Subjects with positive ADA at baseline in whom a titer is not detectable or non-evaluable at a corresponding post-baseline visit is decreased if the ADA turn negative.
- Stable: If ADA titer equal to that at baseline.
- Increased: If ADA titer increasing to a higher titer than that observed at baseline. Subjects with Negative ADA at baseline in whom a titer is not detectable or non-evaluable at a corresponding post-baseline visit is increased if the ADA turn positive.

The titer and the concentration of confirmed positive results will be reported. In addition, confirmed positive ADA samples will be analyzed for their neutralization potential in a neutralizing antibody (NAb) assay.

The incidence of ADA positive subjects and subjects with NAb will be summarized by treatment arms, by visit and overall. Antibody titers will be summarized by median and quartiles by treatment arm and visit.

A listing of immunogenicity data (including titer, concentration, ADA and Nab status) will be provided.

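### The subject-level ADA rate can count antibodies that predate the first study infusion, and no between-arm difference or interval is planned for ADA, NAb or key adverse events

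*Protocol*

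**What the plan says.** **Type of analysis.** Protocol 7.4.1: "The immunogenicity and safety data will be analyzed descriptively". SAP 4 reduces categorical data to counts and percentages. SAP 8.1 adds: "The incidence of ADA positive subjects and subjects with NAb will be summarized by treatment arms, by visit and overall". SAP 9.1.1 to 9.1.9 treat TEAEs, SAEs, infusion-related reactions, hypersensitivity and anaphylaxis in the same way. No table title in SAP 12.2 mentions a difference, ratio or interval. In SAP Table 3 the population-level summary is an incidence (Estimand 1) or a percentage (Estimand 2), although test and reference conditions are both named.

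**Subject-level ADA rule.** SAP 8.1: "A subject is considered as ADA positive during the study if the subjects had at least one ADA positive sample"; otherwise the subject is negative, and unscheduled visits count. The by-visit summary covers the "percent of subject with ADA formation at Day 1 and Day 15, and at weeks 4, 8, 12 (EOS/ET) visit". The Day 1 sample is drawn before dosing (Protocol 6.2.1). Protocol 4.2: "The duration of the study is defined for each subject as the date when signed written ICF is provided through the EOS visit". The study period therefore starts before Day 1.

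**Prior exposure.** Protocol 4.1.1: "Subjects are only eligible if they have received the prior US or EU-rituximab course within the 15 months prior to the date of randomization".

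**Baseline positives.** SAP 8.1: "for subjects who are ADA positive at baseline, a shift table per treatment arm will be generated". Subjects are classed at each post-baseline visit as Decreased, Stable or Increased, and the text for Increased also mentions baseline-negative subjects who turn positive.

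**The concern.** The trial randomises 1:1, stratified by region, and Protocol 3.1.2 says the design lets the DRL_RI arm be assessed relative to control in support of registration.

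Estimand 1 names the development of ADA as its endpoint. The any-positive rule does not measure that. A subject who is positive only before the first study infusion counts the same as one who converts after it. For adverse events the SAP does require emergence: an event that began before dosing counts only if it worsens (SAP 9.1). ADA has no such rule. A chance imbalance in Day 1 positives therefore passes straight into the headline comparison, where it can hide or mimic an effect of the transition.

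Separately, two percentages that look alike do not show how large an increase the data still allow. At this sample size that range is wide.

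**Working it through.** **Inputs.** 70 subjects per arm (Protocol 3.1.1). The documents give no Day 1 ADA prevalence and no 12-week ADA rate. The only background figure is 11% positive on at least one visit, pooled over rituximab trials (Protocol 1.1.1.5). It is not a 12-week rate, so about 4%, 11% and 20% are used as an assumed range. The sample-size justification is redacted; 140 cannot be reproduced and is not disputed.

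**Step 1. Does the plan give post-baseline incidence anywhere?**
- Any-positive row: includes Day 1.
- Day 1 row of the by-visit summary: a rate per arm; it does not show who converted later.
- Table 14.2.2.3 (shift): limited to subjects positive at baseline, so the negative-to-positive converters mentioned under Increased cannot appear in it. It is also by visit, with no roll-up to the subject.
- Immunogenicity population (SAP 4.3.2): requires a post-dose result but keeps Day 1 positives.
- Listing 16.2.6.1: a reader could rebuild the figure subject by subject.

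No planned table gives a subject-level post-baseline incidence.

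**Step 2. Precision of a difference.** The Miettinen-Nurminen limits are the values δ that solve (p1 − p2 − δ) / √{[r1(1−r1)/n1 + r2(1−r2)/n2] × N/(N−1)} = ±1.96. Here r1 and r2 are the maximum-likelihood rates under r1 − r2 = δ, and N = n1 + n2.

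| Counts, 70 per arm | 95% limits (points) |
|---|---|
| 0 vs 0 | ±5.2 |
| 3 vs 3 (4%) | ±8.2 |
| 8 vs 8 (11%) | ±11.2 |
| 14 vs 14 (20%) | ±13.5 |
| 16 vs 16 | ±14.1 |

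Newcombe intervals agree closely: ±8.1, ±11.0 and ±13.3 for 3, 8 and 14 per arm.

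**Step 3. How Day 1 positives can mask a difference (DRL_RI vs reference, assumed counts).**
- Day 1 positives: 4 vs 8. Positive only after dosing: 12 vs 8.
- Any-positive rule: 4 + 12 = 16 vs 8 + 8 = 16. Difference 0.0 (−14.1 to +14.1).
- Day 1 negatives at risk: 70 − 4 = 66 vs 70 − 8 = 62. Converters 12/66 = 18.2% vs 8/62 = 12.9%. Difference +5.3 (−7.7 to +18.2).

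**Step 4. How often such an imbalance arises by chance.** The Day 1 counts are taken as two independent Binomial(70, p) variables.

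| Day 1 prevalence p | Gap of 4 or more, either direction | Gap of 4 or more, the one direction that masks an increase |
|---|---|---|
| 3/70 (4%) | 14% | 7% |
| 11% | 34% | 17% |
| 20% | 46% | 23% |

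**Step 5. Dilution without any imbalance.** With Day 1 positivity b and emergent rate e among Day 1 negatives, the any-positive rate is b + (1 − b)e. Take assumed emergent rates of 10% vs 5% (difference 5.0 points, ratio 2.0) and b = 11%. The any-positive rates are 0.11 + 0.89 × 0.10 = 19.9% and 0.11 + 0.89 × 0.05 = 15.45%, a difference of 4.45 points and a ratio of 1.29. At b = 5% the ratio is 1.49, and at b = 20% it is 1.17.

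**The case against.** The strongest reply is that the plan is openly descriptive and little is hidden. The formal objective is to assess; ruling out change appears only in the rationale (Protocol 1.1.3), and no margin is set. Day 1 ADA is tabulated by arm, so an imbalance would be visible. The listing gives ADA, NAb and titer for each subject, and anyone can compute a crude interval from the planned counts. SAP 8.1 also already recognises rises from baseline at each visit. The masking example is chosen to cancel exactly, and all its rates are assumed.

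Much of this stands. A reader might infer that the trial needs a hypothesis test or a margin; the documents do not support that. A reader might infer that the SAP ignores baseline positives; it does not, since it has the shift table and the Increased class. A reader might also take the either-direction chances in Step 4 as the chance of masking an increase; the one-direction column is the relevant one, and even that is only the chance of an imbalance that size, not of exact cancellation.

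What does not fall away is narrower. Seeing a Day 1 imbalance does not remove it from the headline rate, and the converters have no table to appear in. The report is also not obliged to state any precision. The redacted sample-size text and the table shells, which were not supplied, might contain a precision statement; that cannot be judged.

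**Conclusion.** Both points hold in this limited form. As written, the subject-level ADA rule can count antibodies from before the transition, which does not match Estimand 1. The SAP's own classes for change after baseline are not carried through to a subject-level incidence. The visible text plans no between-arm difference or interval for ADA, NAb or key adverse events; under the assumed rates of 4% to 20% and 70 per arm, that leaves about ±8 to ±13.5 points unstated.

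The pre-dose problem applies to ADA and to NAb, which is tested on the same samples. It does not apply to TEAEs. How much it matters depends on Day 1 prevalence, which the documents do not give; if few subjects are positive on Day 1, the effect is small. This is a change that should be made, not a flaw that invalidates the trial.

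**What to change.** **ADA rows (SAP 8.1; tables 14.2.2.1 and 14.2.2.1A).** Keep the any-positive row and add post-baseline ADA:
- (i) ADA-negative at Day 1 pre-dose with at least one confirmed-positive post-dose sample; denominator, Day 1 negatives.
- (ii) ADA-positive at Day 1 and Increased at any post-baseline visit; denominator, Day 1 positives.
- (i) or (ii) combined; denominator, all subjects with a Day 1 result.

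Use the SAP's any-increase definition. The assay works in steps ("serial 2-fold dilutions of confirmed positive samples will be performed"), so a minimum titer rise may be preferred; if so, apply it to the Increased class in 14.2.2.3 as well, so that the tables agree. Report subjects with no Day 1 result in a footnote. Define post-baseline NAb as NAb-positive after the first infusion and not on Day 1.

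**Differences.** Add the DRL_RI minus reference risk difference with one two-sided 95% Miettinen-Nurminen interval, stratified by region (unstratified if a stratum is too sparse). Do this for any-positive ADA, combined post-baseline ADA, NAb, any TEAE, any SAE, infusion-related reactions, hypersensitivity and anaphylaxis. The adverse-event rows go in 14.3.1.1. Label the intervals descriptive, with no test, margin or multiplicity adjustment. Name the difference in the population-level summary of both estimands.

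**Timing.** SAP 1 ties an addendum to database lock. If lock has passed, use an addendum, labelled post hoc if the data are also unblinded.

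**Cost.** One SAP paragraph, two derived variables, and extra rows or columns in three tables; no new data or subjects. The intervals will read less favourably than bare percentages, and two ADA rows must be explained.

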7.4.2 Missing Data

All efforts will be made to ensure that all values are populated for start and stop date of AE/concomitant medication and severity and causality of AE. In case of any missing or partial dates for AEs, concomitant medication, and any other dates required for analysis still exists, then those will be imputed in an appropriate conservative way. For AEs, missing severity and relationship with treatment, if any, will also be imputed in an appropriate conservative way. Further details will be described in the SAP.

Other missing values will not be imputed, unless otherwise specified in each analysis section.

7.4.3 Demographic and Baseline Characteristics

Demographic and baseline characteristics will be analyzed in a descriptive fashion and results will be presented overall and by treatment arm.

7.4.4 Subject Disposition

The following will be summarized (overall and by treatment arm where applicable):

- Subjects screened.
- Subjects randomized.
- Subjects in the safety analysis set.
- Subjects completing the study/withdrawing early (including withdrawal reason).

7.4.5 Immunogenicity Analysis

The immunogenicity endpoint of this study is the incidence of ADA, including titer and NAb.

Immunogenicity data (ADA and NAb) will be summarized and analyzed descriptively for each scheduled protocol assessment time point by treatment arm and overall.

Further details of the analysis will be described in the SAP.

7.4.6 Safety Analysis

The safety analysis will be based on the safety population and will be analyzed according to the treatment they actually received. Detail methods will be described in the SAP.

The safety endpoints are as follows:

- Incidence of AEs.
- Incidence of anaphylactic reactions, hypersensitivity reactions, and IRRs.

Other safety endpoints will include the following:

- Clinical laboratory parameters
- Vital signs
- Twelve-lead ECG
- Physical examination.

Treatment-emergent AEs will be described using descriptive statistics and coded according to the Medical Dictionary for Regulatory Activities (MedDRA), system organ class and MedDRA preferred term, graded according to CTCAE (Version 5.0 or any latest version), by treatment arm and overall. TEAEs observed, will be summarized separately by treatment arm. Treatment-related TEAEs and SAEs, TEAEs leading to study discontinuation, and deaths will be also summarized by treatment arm.

Incidence of anaphylactic reactions, hypersensitivity reactions, and IRRs will be summarized by treatment arm and overall.

Clinical safety laboratory data will be presented by treatment arm and overall. For each visit, the actual result and the change from baseline will be presented. Shift tables for values outside the clinical normality status will be presented as appropriate.

Otherwise, safety data will be presented in tabular and/or graphical format and summarized descriptively, where appropriate. For continuous measurements (laboratory and vital signs data), change from baseline will be additionally summarized by treatment arm and visit.

Subject listings will be produced for all safety endpoints.

7.4.7 Interim Analyses

There will be no interim analysis in this study.

8 Quality Control and Quality Assurance

This study will be conducted according to the International Council for Harmonisation (ICH) E6(R2) risk and quality processes described in the applicable procedural documents. The quality management approach to be implemented in this study will be documented and will comply with the current ICH guidance on quality and risk management.

8.1 Case Report Forms/Source Data Handling

An eCRF is required and should be completed for each included subject. The investigator shall be provided with standardized eCRF and shall ensure that all data from subject visits are promptly entered into the eCRF in accordance with the specific instructions given.

The investigator must maintain source documents at the study site to support the data entered into the eCRF. Source documents are considered to be all information in original records and certified copies of original records of clinical findings, observations, data, or other activities in a clinical study necessary for the reconstruction and evaluation of the study, such as laboratory reports, edges, consultation reports, complete medical history, and physical examination reports.

The investigator has ultimate responsibility for the collection and reporting of all clinical, safety, and laboratory data entered on the eCRF and any other data collection forms (source documents) and ensuring that they are accurate, authentic/original, attributable, complete, consistent, legible, timely (contemporaneous), enduring, and available when required. The eCRF must be signed by the investigator or by an authorized staff member to attest that the data contained on the eCRF is true.

